Approximately 800,000 individuals in the United States have a heart attack every year, with almost 1 in 4 of those individuals already having suffered a previous heart attack. Attending cardiac rehabilitation (CR) following a cardiovascular event improves cardiorespiratory fitness and health-related quality of life, as well as decreases the risk of future illness and death from heart disease. Unfortunately, once an individual finishes a CR program, continued participation in physical activity (PA) too often reverts to previous sedentary patterns, limiting beneficial health effects. Continued participation in PA post-CR is especially challenging among older adults – likely due to a lack of self-efficacy and confidence in their ability to perform PA due to either their age or other health conditions that make PA more challenging. However, the need to address other health conditions, in conjunction with the benefits of improved strength and mobility, makes continued PA participation following a structured CR program even more useful for older adults. Although individuals typically understand habitual participation in PA is good for their health, we poorly understand why some individuals successfully adhere to and maintain PA habits, while others succumb to barriers preventing them from maintaining the health benefits beyond CR. In addition to understanding factors and triggers influencing PA maintenance beyond CR, little research has developed or investigated interventions targeting this important transition period following structured CR programming to promote continued PA participation “at home”. Therefore, this proposal aims to 1) identify factors and triggers influencing PA participation after a traditional 36-session CR program (Stage 0); and 2) test a targeted health coaching intervention using these identified triggers to optimize PA maintenance and mobility among older adults who completed a center-based CR program.

Design & Procedures

Target-CR will enroll up to 30 adults for this pilot study to identify 26 individuals eligible for participation. The following aims will maximize the value of the data:

Aim 1. To identify factors and triggers influencing PA participation after structured CR among older adults who have enrolled in a center-based CR program.

Aim 2. To compare the effects of a targeted health coaching intervention versus standard care immediately following CR on PA maintenance and functional fitness.

Study Procedures

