Study visits are divided into five phases as detailed below.

Phase 1 – Screening/Consent: The Screening/Consent Phase will be completed virtually or in-person in 1-2 visits depending on scheduling and will take a total of about 1 to 2 hours. During this phase, the participant will be asked to do the following:

- Discuss details of the study with study staff and review/sign the consent form
- Provide contact information
- Review medical history
- Complete Mental Health Screening Questionnaire

Phase 2 – Initial Testing: The Initial Testing Phase involves one in-person visit and will take a total of about 2.5 hours. During this phase, the participant will be asked to do the following:

Qualitative Interview – Participants will complete a qualitative interview assessing factors and triggers influencing current physical activity participation. These sessions will be recorded as audio files for future reference by study staff.

- Measure height and weight
- Review medications
- Complete Paffenbarger Physical Activity Questionnaire
- Senior Fitness Test – Participants will perform a chair stand test, arm curl test, chair sit and reach test, back scratch test, 8-foot up and go test, and step-in-place test.
- Dispense Garmin activity monitor

Phase 3 – Randomization: Upon completion of the Screening/Consent and Initial Testing phases, participants will be randomized to one of two groups:

- Targeted Health Coaching (THC) Group – ~50% of study participants will be in the THC group.
- Standard Care (SC) Group – ~50% of study participants will be in the SC group.

Phase 4 – Intervention: The Intervention Phase will last about 3 months and will be different for the THC and SC groups:

- THC Group – Participants in the THC group will receive an exercise prescription (steps/day) based on their last cardiac rehabilitation session exercise prescription. Participants will be provided a Garmin wearable device to track steps/day. Additionally, participants will partake in 6 virtual or in-person health coaching sessions lasting approximately 30-60 minutes in duration. These sessions will take place approximately every other week during the 3-month intervention period.

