- To inform the health coach what the current barriers and triggers influencing the participant's ability to perform physical activity after structured CR. This will be discussed with the participants randomized to the THC group in their initial health coaching session.
- Develop the common themes of factors and triggers reported in this population. We will conduct a thematic analysis utilizing the baseline qualitative interview transcripts and two personnel. The personnel assigned for thematic interpretation will follow a step-by-step process: 1) familiarization with the transcript data; 2) develop an initial set of codes representing observed data meanings and patterns; 3) collate data excerpts by code; 4) group codes into potential themes; 5) review and revise themes with co-transcribing personnel. From this, we will assess the most common baseline self-reported factors and triggers influencing PA participation. Analyses will be focused on descriptive data including frequencies of the common themes identified.

For Aim 2, our statistical approach will be as follows:

We will classify maintenance in two ways – 1) using mean steps/day over the 3-month intervention period; and 2) calculated as (steps/day completed) divided by (steps/day prescribed) times 100 and average this metric over the 3-month study period. Data will be analyzed using Intent-to-Treat and statistical significance will be set at 0.05. We will assess the following:

Primary outcome: Within-group differences in maintenance metrics and Senior Fitness test scores (THC group n=13 vs. SC group n=13). Using 80% power at alpha level 0.05, we should be able to detect an effect size around 0.62 for analyses of pre-to-post change scores using steps per day as the primary outcome using paired t-tests, paralleling published findings.

Secondary outcome: Between-group differences in maintenance metrics and Senior Fitness Test scores (13 vs. 13)

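### The primary analysis tests change within each arm, so it cannot answer Aim 2, which compares coaching with standard care between randomised arms

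*Combined protocol and SAP*

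**What the plan says.** Under Design & Procedures, Aim 2 is "To compare the effects of a targeted health coaching intervention versus standard care immediately following CR on PA maintenance and functional fitness". Study Procedures, Phase 3, randomises participants to two groups of about half each, and Data Analysis & Statistical Considerations targets 13 per group.

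For Aim 2 the analysis section then states:

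- "Primary outcome: Within-group differences in maintenance metrics and Senior Fitness test scores (THC group n=13 vs. SC group n=13". The accompanying power sentence claims 80% power at alpha 0.05 for an effect of about 0.62, "for analyses of pre-to-post change scores using steps per day as the primary outcome using paired t-tests".
- "Secondary outcome: Between-group differences in maintenance metrics and Senior Fitness Test scores (13 vs. 13". Nothing more is said about this contrast: no test, model, detectable effect or interval.

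Maintenance is measured in two ways: "using mean steps/day over the 3-month intervention period", and a percentage "calculated as (steps/day completed) divided by (steps/day prescribed) times 100 and average this metric over the 3-month study period". The same section says that the pilot data will feed effect sizes and power for future studies, but not which estimate will be used.

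**The concern.** The aim and the design are comparative, but the primary analysis is not. The vs. in the primary line does not make it a comparison of arms: the line says within-group, the test is paired, and the between-group difference is listed separately as secondary.

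Under Study Procedures, both arms receive a step prescription derived in the same way from the last rehabilitation session, a Garmin and repeat testing. Both also move further from the end of rehabilitation. A change within the THC arm contains all of this as well as coaching.

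Background & Significance says that after rehabilitation "continued participation in physical activity (PA) too often reverts to previous sedentary patterns". If that happens here, coaching may work by preventing a decline. THC's own change would then be near zero, and the primary results would bear on coaching only if a reader set one arm's p-value against the other's. The plan does not state that inference, but primary results reported arm by arm offer no other route to one.

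The primary test is also incompletely defined for the step metrics. Both are averages over the intervention, and no baseline step-count period is specified for a paired test. One would be possible, because Phase 2 includes "Dispense Garmin activity monitor". The between-group contrast does not need one.

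**Working it through.** **Inputs from the documents:** 13 per group, alpha 0.05, 80% power, stated effect about 0.62, paired t-test. **Assumptions:** two-sided testing (sidedness is not stated), 13 analysed per arm, and the correlations and true changes marked below.

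**1. The plan's own figure.** For a paired t-test, power = P(|T| > t(0.975, n−1)), where T is noncentral t with n−1 df and noncentrality d√n; d is in SD of within-person change.

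- n = 13: at d = 0.62 the noncentrality is 0.62 × √13 = 2.24 and power is 54%. The detectable d at 80% power is 0.847 (0.732 if one-sided).
- n = 26, both arms pooled: detectable d = 0.572.
- n = 22: power at 0.62 is 79.2%. n = 23: 81.1%.

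So 0.62 fits neither 13 nor 26. It fits about 22–23 pairs, a number the plan does not give.

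**2. The comparison Aim 2 asks for.** For a two-sample t-test, 13 vs 13, df = 24 and the standard error is √(2/13) = 0.392 in between-person SD.

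- Detectable difference at 80% power: 1.145 SD.
- 95% CI half-width: t(0.975, 24) × 0.392 = 2.064 × 0.392 = 0.81 SD.

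For Senior Fitness Test scores with baseline adjustment (ANCOVA, 23 df), the residual SD is √(1−r²). The documents give no baseline-to-follow-up correlation r, so a range is shown; chance baseline imbalance is ignored.

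| Assumed r | Detectable difference (SD) | 95% CI half-width (SD) |
|---|---|---|
| 0.5 | 0.994 | 0.703 |
| 0.7 | 0.819 | 0.579 |
| 0.8 | 0.689 | 0.487 |

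These are on the between-person scale. The 0.62 is on the within-person-change scale, so the two should not be compared directly.

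**3. What arm-by-arm reading would do.** This illustration applies only to outcomes with a baseline value. Suppose both arms share the same true decline d (an assumption), so coaching has no effect. The arms are independent, so P(SC declines significantly, THC not significant) = P(significant decline) × (1 − p), where p is the two-sided paired power at n = 13.

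| Shared decline d (SD of change) | p | P(SC significant, THC not) |
|---|---|---|
| 0 | 0.050 | 2.4% |
| 0.1 | 0.063 | 4.9% |
| 0.2 | 0.102 | 8.8% |
| 0.3 | 0.169 | 13.9% |
| 0.5 | 0.382 | 23.6% |
| 0.62 | 0.538 | 24.9% |
| 0.85 | 0.803 | 15.8% |
| 1.0 | 0.911 | 8.1% |

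At d = 0.62, for example, 0.538 × 0.462 = 0.249. Because p(1 − p) cannot exceed 0.25, 25% is a ceiling, and with no common change there is no inflation. Simulation with 200,000 trials at each d agreed to within 0.1 percentage point. In the same trials a two-sample test favoured THC 2.5–2.6% of the time.

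**4. Coaching that fully prevents the decline (an assumption).** THC's true change is then 0, so its paired test is significant 5% of the time, however large the decline prevented.

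**The case against.** The strongest reply is that the randomised contrast is already planned, on the same outcomes, by intention to treat at 0.05. Nothing is left uncollected, and in a pilot of about 26 both contrasts will be reported whatever their labels. It is true that the comparison is planned. But it has no named test or stated precision, and the result designated primary still does not address the aim. Pilot status excuses low power, not a primary contrast that misses the question.

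Second, the 2.4% to 25% series depends on an inference the plan never states, and it does not apply to the step metrics as now defined. The background text describes a general tendency; it does not forecast a mean decline in this trial. All of this stands. The series is a conditional illustration, and the conclusion does not depend on it.

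Third, the remedy leaves other matters open:

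- Two step metrics and six Senior Fitness Test items make eight primary tests. If they were independent (an assumption), the chance of at least one false positive would be 1 − 0.95⁸ = 34%. The plan already has this multiplicity, and changing the contrast does not add to it.
- Dropout would worsen precision. With an assumed 11 per arm, the detectable difference is 1.26 SD and the half-width 0.89 SD.
- The prescribed steps/day could serve as a covariate for mean steps/day, although they are not a measured baseline.
- If outcome data have already been examined, promoting the between-group contrast is a post hoc change and must be disclosed as one.

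These are fair refinements. None removes the mismatch.

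**Conclusion.** The concern holds and must be fixed. Followed exactly, the plan yields a headline result that does not estimate the effect of coaching, while the contrast that does is a secondary line without a test or precision. That conclusion follows from the text alone and needs no assumption.

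The sizes do rest on assumptions. With two-sided testing and 13 analysed per arm, the needed comparison detects about 1.15 SD unadjusted, or about 0.99 to 0.69 SD for baseline-adjusted fitness scores if r is 0.5 to 0.8. Independently of this, the stated 0.62 is not what 13 per group delivers for a paired test. A future two-arm trial would need the between-group estimate for its sample size, and the plan does not commit to using it.

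**What to change.** In Data Analysis & Statistical Considerations, Aim 2:

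- Make THC minus SC the primary contrast for the outcomes now listed as primary, each with a named test and 95% CI: a two-sample comparison (e.g. t-test) for mean steps/day and for percentage of prescribed steps, and a baseline-adjusted comparison (e.g. ANCOVA) for Senior Fitness Test scores. Steps/day, which the power sentence already treats as the primary outcome, can be the lead metric.
- Report within-group changes descriptively, where a baseline value exists.
- State that significance in one arm and not in the other supports no conclusion about coaching.
- Replace the power sentence with the between-group precision, giving its assumptions.
- State that effect sizes for future trials will use the between-group estimate and its CI.
- Date the change and say whether any outcome data had been seen.

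This needs no new data, visits or participants, and no listed outcome is demoted. The price is a less favourable stated detectable effect, about 1.15 between-person SD unadjusted, which is acceptable for a pilot focused on estimation.

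### The primary outcome line and the power sentence describe different quantities, and the powered one, a pre-to-post change in steps per day, has no stated measurement windows

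*Combined protocol and SAP*

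**What the plan says.** All of the following is under Data Analysis & Statistical Considerations, Aim 2, unless noted.

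- **Step metrics.** Maintenance is classified in two ways. The first is defined "using mean steps/day over the 3-month intervention period". The second is completed steps as a percentage of prescribed steps, and the plan will "average this metric over the 3-month study period".
- **Primary outcome.** "Within-group differences in maintenance metrics and Senior Fitness test scores", with 13 participants in each arm.
- **Power sentence.** It follows directly and gives 80% power at alpha 0.05 for an effect size around 0.62, for "analyses of pre-to-post change scores using steps per day as the primary outcome using paired t-tests".
- **Secondary outcome.** "Between-group differences in maintenance metrics and Senior Fitness Test scores".
- **Significance.** "statistical significance will be set at 0.05". Sidedness is not given, and nothing says which arm or measure the level applies to.
- **Fitness tests.** Study Procedures, Phase 2, lists the "chair stand test, arm curl test, chair sit and reach test, back scratch test, 8-foot up and go test, and step-in-place test". No composite score is defined.
- **Step recording before the intervention.** For steps, Phase 2 says only "Dispense Garmin activity monitor". Phase 6 repeats the initial tests, without the interview.

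**The concern.** Two adjacent statements name different primary quantities. The outcome line covers eight measures (two step metrics and six fitness tests) within each arm. The power sentence covers one measure, steps per day, as a paired change. A paired test needs two values per participant, and each step metric supplies one, taken while the intervention is running.

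The choice of contrast also matters. Aim 2 asks how coaching compares with standard care. Background & Significance expects activity to fall back after rehabilitation, so an arm that simply holds its level while the other declines would be a success. A within-arm change test is not built to show that.

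At stake is whether a reader can tell, before the data are seen, which result the 0.05 and the 80% power refer to, and which measure and contrast will supply the effect size for the next study.

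**Working it through.** **1. Is the powered quantity defined?** Setting the sections side by side:

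| Quantity | Pre value | Post value |
|---|---|---|
| Metric 1, average daily steps | none stated | one average across the three months |
| Metric 2, percent of prescribed steps | none stated | one average across the three months |
| Six fitness tests | Phase 2 visit | Phase 6 visit |
| Change in steps per day (power sentence) | none stated | none stated |

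The monitor is handed out before randomization, so a pre-intervention window would be feasible, but the plan does not describe one. The physical activity questionnaire is completed at both visits, but it is not described as a steps measure and the Aim 2 analysis does not use it. The gap therefore concerns steps only; the fitness changes can be computed.

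**2. The plan's 0.62.** Inputs from the plan: paired t-test, 13 per arm, alpha 0.05, power 80%. Sidedness is not stated, so both are tried. Power comes from the noncentral t distribution with df = n − 1 = 12 and noncentrality d × √n, where d is in SDs of the change score.

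- Solving for d at 80% power with n = 13: **0.847 two-sided, 0.732 one-sided**.
- Normal approximation, (z for alpha + z for power)/√13: 0.777 two-sided, 0.690 one-sided.
- Power at d = 0.62, where noncentrality = 0.62 × √13 = 2.24: **54% two-sided, 68% one-sided**.
- Pooling all 26 as pairs: 0.572 two-sided, 0.501 one-sided.
- Pairs needed for at least 80% power at 0.62: 23 two-sided, 18 one-sided. Neither number is in the plan.

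None of these gives 0.62 from the stated inputs. One route does. If 0.62 is in raw between-person SDs and ρ is the pre-post correlation, then d = 0.62/√(2(1 − ρ)). Setting d = 0.847 gives ρ = 1 − (0.62/0.847)²/2 = 0.73; setting d = 0.732 gives ρ = 0.64. The plan refers to published findings but gives no correlation or SD.

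**3. Two arms at 0.05.** If steps per day is tested within each arm and neither arm truly changes, the chance of at least one significant result is 1 − 0.95² = **9.75%**.

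**4. Holding steady.** If the coaching arm's true change in steps is zero, its paired test is significant with probability equal to alpha, 5%, however far standard care declines.

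**5. The between-group comparison already planned.** Two-sample t-test, 13 vs 13, df = 24, two-sided 0.05, unadjusted:

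- Detectable difference at 80% power: **1.145 SD**.
- 95% CI half-width: t(0.975, 24) × √(2/13) = 2.064 × 0.392 = **0.81 SD**.
- Standard error of a chance difference between arms at baseline: √(2/13) = **0.39 SD**.

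**The case against.** **This is a pilot.** Its data are meant to inform effect sizes and power for later work, and it states no confirmatory claim or go/no-go rule. That stands and lowers the stakes. It does not remove the need for the plan's own primary outcome, alpha and power claim to describe the same thing.

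**The power sentence already signals one lead measure.** Its wording on steps per day is fair evidence that a single measure is meant to lead. The change, its windows and the arm are still missing.

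For the same reason, a reader might count eight measures in two arms as 16 primary tests and quote a large overall false-positive rate. The documents do not support that. No rule declares success on any one positive result, the power sentence points to steps, and step-change tests cannot be counted while the change is undefined.

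**The comparison with standard care is planned.** A reader might infer that the arms will be judged by setting one arm's p-value against the other's. The plan does not say so; it lists the direct comparison, though only as secondary.

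**Percent of prescribed steps gives a within-arm reference.** Each prescription derives from the participant's last rehabilitation session, so an arm near 100% can be read as keeping to its target. It would therefore be too strong to say that only the between-group comparison could show a benefit. A prescription is still not a measured baseline, and it does not supply the missing pre value.

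**Reversing primary and secondary is not strictly required.** That is correct. The inconsistency can also be cured within the sponsor's order, and the fix gives that route.

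**Conclusion.** The point holds and should be corrected. The outcome line and the power sentence disagree on what is primary. The paired steps test cannot be run from the plan as written, because neither step window is stated. The arm carrying the 0.05 is not named, at a cost of 9.75% against 5% if steps are tested in both. The primary contrast does not answer Aim 2.

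The 0.62 does not follow from 13 pairs. The matching figure is 0.85 SD of change two-sided or 0.73 one-sided, assuming normal change scores, no dropout and an effect scaled by the SD of change. A reader might infer that 0.62 is simply an arithmetic slip. The documents do not settle that, since raw-SD scaling with a correlation of about 0.73 (0.64 one-sided) would yield it; neither assumption is stated.

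The mismatch in definitions does not depend on the 0.62 being wrong.

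**What to change.** **Preferred.** Make average daily steps across the three intervention months, coaching versus standard care, the single primary comparison at 0.05. Adjust for prescribed steps per day, using the initial prescription that every participant in both arms receives. Report the estimate with a 95% CI. Report percent of prescribed steps, the six fitness tests and all within-group changes as secondary. Replace the power sentence: unadjusted, 13 vs 13 has 80% power for about 1.15 SD, with a 95% CI half-width of about 0.81 SD.

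**Cost.** Protocol wording only; no new data or participants. There are four downsides:

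- Power is low, so the result is best read as an estimate.
- The fitness tests, which Aim 2 names alongside activity, lose primary status.
- The sponsor's primary/secondary order is reversed.
- With no measured baseline, chance imbalance has a standard error of about 0.39 SD, which adjustment for prescribed steps addresses only in part.

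**Alternative that keeps the sponsor's order.** Define the pre-intervention and end-of-intervention windows for steps per day. Name the one measure and the one arm that carry the 0.05. Restate the detectable effect for 13 pairs as about 0.85 SD of change, two-sided. If 0.62 is kept, state the scaling, the correlation and its source. This route needs a defined period of monitor wear before the intervention, and the comparison in Aim 2 stays secondary.

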- Integrative Health Coaching Mental Health Screening Questionnaire score >4 (screening), if not currently in treatment
- Participation in an inpatient substance abuse rehabilitation program within one year
- Exclusion criteria will primarily be identified by way of a phone screen process conducted by a designated member of the study team; however, medical record review may be used to confirm the presence/absence of certain medical conditions listed as inclusion/exclusion criteria.

Subject Recruitment and Compensation

Potential subjects for this study will be recruited from the Duke Cardiopulmonary Rehabilitation clinic at Croasdaile. Potential participants will initially be identified by study staff and cardiac rehab staff familiar with the study. The study may be introduced to the potential participant during the course of their cardiac rehabilitation program or they may be contacted by phone, email or snail mail after they have completed their cardiac rehab program.

The PI will coordinate with the Clinical Operations Supervisor and Manager of the Cardiopulmonary Rehabilitation clinic to identify patients approaching the completion of their cardiac rehabilitation program who may be interested in the research study. If the individual meets most of the inclusion/exclusion criteria, the subject will be invited to attend a private study information session conducted by the PI or designated member of the study team to learn the details of the study. We will allow up to 60 minutes for the subjects to read the consent, ask questions and decide whether or not they are willing to participate in the study.

Participants will receive compensation for completing each scheduled study visit for a maximum of \$150. In addition, participants will keep the wearable device (\$165/device) they were provided for the intervention.

Data Analysis & Statistical Considerations

The Target-CR study will collect both qualitative and quantitative data, utilizing demographic, behavioral/psychosocial, activity, and functional fitness measurements. This is a pilot intervention trial, thus the number of subjects randomized will be ~26 across the 1-year funding period with a target of 13 participants in each group. Given this is a pilot grant, this data will be utilized for future study development of effect sizes and power.

Data from Aim 1 will be utilized in two ways:

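### With 13 participants per group, the paired t-test has 80% power for a standardised change of about 0.85 (two-sided), not the stated 0.62, at which power is about 54%

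*Combined protocol and SAP*

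**What the plan says.** The Data Analysis & Statistical Considerations section sets the size of the trial: "the number of subjects randomized will be ~26 across the 1-year funding period with a target of 13 participants in each group". For Aim 2 it states that "statistical significance will be set at 0.05", without saying whether tests are one- or two-sided.

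The primary outcome is given as "Within-group differences in maintenance metrics and Senior Fitness test scores (THC group n=13 vs. SC group n=13". The next sentence is the only power statement in the plan: "Using 80% power at alpha level 0.05, we should be able to detect an effect size around 0.62 for analyses of pre-to-post change scores". The outcome it names is daily steps, and the test it names is the paired t-test. It adds that this is in line with published findings, but gives no standard deviation, pre-post correlation or dropout rate. It does not say that the two groups are combined for the calculation. The between-group comparison is secondary and has no power figure.

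**The concern.** Test, group size, alpha and power are all given, so the detectable effect can be checked directly. A paired t-test on 13 pairs is a small test, and 0.62 looked too small a change for it to detect with 80% power.

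At stake is how the primary result will be read. If a group shows no significant change, a reader who relies on the plan will think a change of 0.62 had an 80% chance of being found, when the real chance is much lower. The plan also intends the pilot to inform effect sizes and power for later studies. A wrong relation between sample size and detectable effect, if carried forward, would make a later trial too small.

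**Working it through.** **Inputs**
- n = 13 pairs per group, from the primary outcome definition.
- Power 80% and alpha 0.05, from the power sentence ("Using 80% power at alpha level 0.05").
- Paired t-test on change scores, from the same sentence. The effect size is therefore read as d = mean change / SD of change.
- Sidedness is not stated. Two-sided is assumed, with one-sided as a check.

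**Formula.** For n pairs the test statistic has df = n − 1 and noncentrality δ = d√n. Two-sided power is P(|T| > t₀.₉₇₅,df), where T follows the noncentral t distribution with noncentrality δ. The detectable effect is the d at which power equals 0.80.

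**Trying to reproduce 0.62 at n = 13**
- Exact t, two-sided: df = 12, critical value 2.179. Power reaches 80% at d = 0.847.
- At d = 0.62: δ = 0.62 × √13 = 2.235, and power = 53.8%.
- Ratio: 0.847 / 0.62 = 1.37, so the detectable effect is 37% larger than stated.
- Normal approximation, two-sided: (1.960 + 0.842)/√13 = 0.777.
- Exact t, one-sided: critical value 1.782, detectable d = 0.732, power at 0.62 = 67.8%.
- Normal approximation, one-sided: (1.645 + 0.842)/√13 = 0.690.

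No change-score calculation at n = 13 gives 0.62. The most lenient gives 0.69.

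**What would give 0.62** (exact t, two-sided unless noted)

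| Pairs | Detectable d | Power at 0.62 |
|---|---|---|
| 13 | 0.847 | 53.8% |
| 15 | 0.778 | 60.8% |
| 22 | 0.626 | 79.2% |
| 23 | 0.611 | 81.1% |
| 26 | 0.572 | 86.0% |
| 30 | 0.529 | 90.7% |

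- The smallest n with at least 80% power at 0.62 is 23 pairs, or 18 if one-sided.
- The row for 15 covers all 30 enrolled, split equally. Design & Procedures says up to 30 are enrolled in order to find 26 eligible, so the extra four are a screening allowance.
- About 22 pairs would mean pooling both arms after some loss. That is not a within-group analysis, and the plan describes neither pooling nor a loss rate.
- In raw-SD units, with equal SDs before and after, d(raw) = d(change) × √(2(1 − r)). Setting 0.62 = 0.847 × √(2(1 − r)) gives r = 1 − (0.62/0.847)²/2 = 0.73 (0.64 if one-sided). No correlation is stated, and the sentence ties the effect size to change scores.

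**Related figures**
- Between groups, 13 versus 13: df = 24, δ = d√(13/2). The detectable difference is 1.145 SD. At 0.62, δ = 1.581 and power is 32.9%.
- Loss after randomisation, with two per arm as an assumption: n = 11, detectable within-group change 0.94, power at 0.62 46%.

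**The case against.** The strongest case against concerns weight, not arithmetic. The number randomised is justified by pilot status and the funding period, not by 0.62, so correcting the figure changes no enrolment, test or estimate. The plan's declared use of the data is to inform later studies, and nowhere does it say that a null result will be used to rule out an effect. This stands, and it lowers the practical consequence. It does not make the power statement correct.

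A second objection is that 0.85 and 54% depend on a two-sided test, that the power sentence carries no n of its own, and that 0.62 may come from a published source or an undisclosed correlation. The dependence on sidedness is real and is stated here, but one-sided testing does not recover 0.62. The n of 13 stands in the immediately preceding sentence. Published findings may explain why 0.62 is of interest; they cannot give 13 pairs more power.

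Third, the between-group figure and the allowance for loss are omissions, not arithmetic errors. That is fair. They are included because they belong in the same corrected sentences, and because the between-group comparison is the one that answers Aim 2.

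Fourth, the sentence concerns pre-to-post change in steps per day, yet the plan describes no step count before the intervention. The Garmin is handed out at initial testing, and both maintenance metrics are averages over the 3-month intervention. This point stands and affects the fix: a corrected figure should be attached to an outcome measured at both visits, such as the Senior Fitness Test, unless a baseline step count is defined.

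**Conclusion.** The concern holds. As written, the plan claims a power property that the design does not have. For a within-group paired t-test on 13 pairs, assuming two-sided alpha 0.05 and an effect size in units of the SD of change, the detectable effect at 80% power is 0.85 and power at 0.62 is 54%. With a one-sided test the figures are 0.73 and 68%. The claim could be rescued only by pooling about 22 pairs across arms, or by using raw-SD units with a correlation near 0.73, and the plan states neither. The arithmetic is certain; where 0.62 came from is not known.

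**What to change.** Replace the power sentence with text such as: *With 13 participants per group and two-sided alpha 0.05, a paired t-test has 80% power for a within-group change of 0.85 SD of the change scores. The between-group comparison (13 versus 13) has 80% power for a standardised difference of 1.15.*

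If the sponsor wishes to keep 0.62, the plan should state the pooling or the pre-post correlation behind it, and the units of the effect size.

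In either case:
- Give the same figures for the expected number of completers.
- Name the outcome to which the paired figure applies. If that is steps per day, define the baseline value.

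The cost is one or two sentences on power, plus a line on the baseline if steps per day is kept. Enrolment and conduct do not change. The stated sensitivity becomes less favourable, which is acceptable in a pilot.
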